5. SAMPLE SIZE CONSIDERATIONS

Sample size calculations are based on the assumption of detecting a 50% reduction in the cumulative proportion of subjects who experience BV recurrence by 12 weeks post-administration of study product among subjects receiving LACTIN-V compared to those receiving placebo in a complete case analysis at the 0.05 significance level. The proportion of subjects among controls who will experience BV recurrence at 12 weeks is assumed to be 30%. We assume a LACTIN-V to placebo allocation ratio of 2:1 and 10% of subjects drop-out from the Complete Case population. Given logistical and feasibility constraints on the sample size and that this is a Phase II-b trial, which will provide screening evidence about safety and efficacy for a subsequent Phase III trial, this trial is powered at the 70% level. Given the assumptions above, a sample size of 228 subjects is required to detect a 50% reduction in the cumulative proportion of subjects experiencing recurrence in the Complete Case population with 70% power using the Pearson Chi-Square test.

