6. GENERAL STATISTICAL CONSIDERATIONS

6.1. General Principles

Tabulations will be used extensively to summarize the data. All continuous variables will be summarized using the following descriptive statistics: n (sample size), mean, standard deviation, median, maximum, and minimum. The frequency and percentages (based on the sample size) of observed levels will be reported for all categorical measures. Wilson confidence intervals for binomial proportions and differences in binomial proportions will be computed for efficacy variables. Blaker confidence intervals for binomial proportions and differences in binomial proportions will be computed for safety variables. For the hypothesis tests comparing treatment groups with respect to safety outcomes, the two-sided Fisher's Exact test will be used. For the hypothesis tests comparing treatment groups with respect to efficacy outcomes, the two-sided Chi-Square test will be used. For all tests, a 5% two-sided significance level will be used.

For all efficacy outcome measures, the Complete Case population (see Section 6.3) will be used as the primary analysis population and the Per Protocol, modified Intent-to-Treat, and Intent-to-Treat populations will be used as secondary analysis populations. For all safety analyses, the Safety population will be used as the analysis population.

All summary tables will be structured with a column/sub-table for each treatment group (LACTIN-V, Placebo, and All Subjects). In general, all data will be listed by treatment group and/or subject, and when appropriate by visit number within subject. The total population size relevant to that table/column if applicable, including any missing observations will be displayed in the tables.

Note that in the data listings, Subject ID is the unique subject identifier, not the Study ID used on study and dates will not be included, only Study Day. Study Day 1 will be the day of the first dose of treatment.

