6.4. Covariates and Subgroups

The protocol does not define any formal subgroup hypothesis tests, and the study is not adequately powered to perform formal subgroup hypothesis testing. However, safety and enrollment summaries will be presented by clinical site. In addition, summaries of colonization will be presented by subgroups defined by menses and sexual intercourse variables (see Section 8.2).

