where $g(\cdot)$ is the logit function, Y_{ij} is the BV diagnosis status of subject i at visit j , δ_i is the indicator function for the treatment group of subject i ($\delta_i = 1$ for LACTIN-V and $\delta_i = 0$ for Placebo), and t_{ij} is time (in study days) at which visit j occurred for subject i . The visits included in the model will be Visit 2 (Week 4) through Visit 4 (Week 12) and each subject will be included from the time of the first administration of study product to the earliest of the following: Visit 4 date, date of exclusion from the particular analysis population, or the termination date. Generalized Estimating Equations will be used to fit the model and estimate its parameters. The following working correlation structures will be explored for the assumed covariance among responses within a subject: independent, exchangeable, unstructured, and first-order autoregressive. Model estimates will be compared informally to assess robustness of the estimates with respect to choice of correlation structure. QIC will be also be used to assess model fit with regard to the correlation structure. The model with the lowest QIC will be reported. If inferential differences between the models, this will be noted in the CSR. [Table 68](#) will present the treatment group-specific odds of BV (and 95% confidence interval) along with the odds ratio between treatment groups (and 95% confidence interval).

Select outcome measures will be further broken down by race as an exploratory analysis. Race will be categorized as Black/African American, White, and Other. The following summaries will be generated:

- BV recurrence by Visit 4 (Week 12) by analysis population, treatment group, and race ([Table 69](#)). Analyses will follow those for [Table 11](#).
- BV recurrence by Visit 7 (Week 24) by analysis population, treatment group, and race ([Table 70](#)). Analysis will follow those for [Table 12](#).
- *L. crispatus* colonization through Visit 4 (Week 12) by analysis population, treatment group, and race ([Table 71](#)). Analysis will follow those for [Table 21](#).

-
- *L. crispatus* colonization at Visit 7 (Week 24) by analysis population, treatment group, and race (Table 72). Analyses will follow those for Table 22.
 - *L. crispatus* CTV-05 concentration by study day, treatment group, and race (Table 73, Table 74, Table 75, and Table 76). Analysis will follow those for Tables 27 – 30.

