	All Subjects	x	x.xx	x.xx, x.xx	--	--
CC	LACTIN-V	x	x.xx	x.xx, x.xx	x.xx	x.xx, x.xx
	Placebo	x	x.xx	x.xx, x.xx	--	--
	All Subjects	x	x.xx	x.xx, x.xx	--	--
PP	LACTIN-V	x	x.xx	x.xx, x.xx	x.xx	x.xx, x.xx
	Placebo	x	x.xx	x.xx, x.xx	--	--
	All Subjects	x	x.xx	x.xx, x.xx	--	--

Table 69: BV Recurrence by Visit 4 (Week 12) by Analysis Population, Treatment Group, and Race

Analysis Population	Treatment Group	Race	Number of Subjects with BV Recurrence n	Number of Subjects N	Proportion of Subjects with BV Recurrence	BV Recurrence 95% CI ¹	Odds of BV Recurrence in LACTIN-V Group Compared to Placebo Group	Odds of BV Recurrence in LACTIN-V Group Compared to Placebo Group 95% CI ²	p-value ³
ITT (LOCF)	LACTIN-V	Black/African American	x	x	0.xx	0.xx, 0.xx	x.xx	x.xx, x.xx	0.xxx
		White	x	x	0.xx	0.xx, 0.xx	x.xx	x.xx, x.xx	0.xxx
		Other	x	x	0.xx	0.xx, 0.xx	x.xx	x.xx, x.xx	0.xxx
	Placebo	Black/African American	x	x	0.xx	0.xx, 0.xx	--	--	
		White	x	x	0.xx	0.xx, 0.xx	--	--	
		Other	x	x	0.xx	0.xx, 0.xx	--	--	
	All Subjects	Black/African American	x	x	0.xx	0.xx, 0.xx	--	--	
		White	x	x	0.xx	0.xx, 0.xx	--	--	
		Other	x	x	0.xx	0.xx, 0.xx	--	--	

Continue for mITT (LOCF), ITT (Worst Case), mITT (Worst Case), CC, and PP populations

Note: The denominator for rate estimates is based on the number of subjects in the respective treatment group, race group, and analysis population.

1: 95% CI= 95% Wilson confidence interval

2: Difference in 95% CI=asymptotic 95% CI from a Chi-Square test

3: p-value calculated from the Chi Square Test.

Table with similar format:

Table 70: BV Recurrence by Visit 7 (Week 24) by Analysis Population, Treatment Group, and Race

Table 71: *L. crispatus* Colonization through Visit 4 (Week 12) by Analysis Population, Treatment Group, and Race

Analysis Population	Treatment Group	Race	Number of Subjects with Colonization n	Number of Subjects N	Proportion of Subjects with Colonization	Colonization 95% CI	Odds of Colonization in LACTIN-V Group Compared to Placebo Group	Odds of Colonization in LACTIN-V Group Compared to Placebo Group 95% CI	p-value ¹
ITT	LACTIN-V	Black/African American	x	x	0.xx	0.xx, 0.xx	x.xx	x.xx, x.xx	0.xxx
		White	x	x	0.xx	0.xx, 0.xx	x.xx	x.xx, x.xx	0.xxx
		Other	x	x	0.xx	0.xx, 0.xx	x.xx	x.xx, x.xx	0.xxx
	Placebo	Black/African American	x	x	0.xx	0.xx, 0.xx	--	--	
		White	x	x	0.xx	0.xx, 0.xx	--	--	
		Other	x	x	0.xx	0.xx, 0.xx	--	--	
	All Subjects	Black/African American	x	x	0.xx	0.xx, 0.xx	--	--	
		White	x	x	0.xx	0.xx, 0.xx	--	--	

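### The race tables (SAP 8.3, Tables 69–72) print a LACTIN-V versus placebo p-value in each race group but no treatment-by-race test, so they cannot show whether the effect differs by race

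*SAP*

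**What the plan says.** SAP 8.3 introduces the race breakdown with "Select outcome measures will be further broken down by race as an exploratory analysis". Race has three levels: Black/African American, White and Other. BV recurrence by Visit 4 (Table 69) and by Visit 7 (Table 70) are to be analysed as in Tables 11 and 12. Colonization through Visit 4 (Table 71) and at Visit 7 (Table 72) are to be analysed as in Tables 21 and 22. All four parent tables carry an odds ratio, a confidence interval and a chi-square p-value for LACTIN-V against placebo.

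The shells in SAP Appendix 1 follow that instruction. In Table 69 each race row has its own odds ratio, interval and p-value, with the footnote "p-value calculated from the Chi Square Test". The block is repeated for six population and imputation combinations. Table 71 has the same layout for four populations. SAP 6.1 adds: "For all tests, a 5% two-sided significance level will be used". SAP 6.8 plans no multiplicity adjustment.

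On subgroups, SAP 6.4 says that "the study is not adequately powered to perform formal subgroup hypothesis testing". It then lists the subgroup summaries it allows, which are by clinical site and by menses and intercourse. Race is not in the list. The only interaction term in the SAP is treatment by time, in the repeated-measures model of section 8.3.

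**The concern.** The specific question for a race breakdown is whether the treatment effect differs between groups. A p-value inside each group tests something else: whether that group alone departs from no effect. Whether it falls below 0.05 depends heavily on group size. When groups are small and unequal, a common effect will often reach significance in one and miss it in another, and that pattern is easily taken for a difference.

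The trial is meant to inform a Phase III study. A table that appears to show benefit in one race and none in another could influence who is enrolled next and how the product is described. The plan offers no test against which to check such a reading and no rule for interpreting the p-values.

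**Working it through.** **Inputs.** From SAP 5: control recurrence 30%; "detecting a 50% reduction in the cumulative proportion of subjects who experience BV recurrence by 12 weeks", hence 15% on LACTIN-V; "We assume a LACTIN-V to placebo allocation ratio of 2:1 and 10% of subjects drop-out from the Complete Case population"; 228 randomized; "this trial is powered at the 70% level". From SAP 6.1: two-sided 5%. The sizes of the race groups are not in the documents, so every split below is an assumption.

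**1. Reproduce the plan's sample size.** With 2:1 allocation the pooled rate is (0.30 + 2 × 0.15)/3 = 0.20. The number on placebo is

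[1.96 × √(1.5 × 0.20 × 0.80) + 0.524 × √(0.30 × 0.70 + 0.15 × 0.85/2)]² / 0.15² = (0.960 + 0.274)² / 0.0225 ≈ 67.7, so 68.

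The total is 3 × 68 = 204. Allowing for 10% dropout, 204/0.9 = 226.7, so 227, or 228 as a multiple of three. This is the plan's figure. About 228 × 0.9 = 205 women are evaluable, and exact Pearson power at 137 against 68 is 0.706.

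**2. Power within each race under a uniform effect.** For group sizes n_L and n_P, power is the sum of Bin(a; n_L, 0.15) × Bin(b; n_P, 0.30) over all outcomes (a, b) at which the Pearson statistic exceeds 3.84. With an assumed 50/30/20 split of 205 women:

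| Group | LACTIN-V / placebo | Exact power |
|---|---|---|
| Largest | 68 / 34 | 0.447 |
| Middle | 41 / 21 | 0.299 |
| Smallest | 27 / 14 | 0.219 |

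**3. Chance of a mixed pattern.** The groups contain different women, so their tests are independent.

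- All significant: 0.447 × 0.299 × 0.219 = 0.029.
- None significant: 0.553 × 0.701 × 0.781 = 0.303.
- At least one significant and at least one not: 1 − 0.029 − 0.303 = 0.668.

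**4. Sensitivity to the split** (same effect, 205 women). The mixed pattern occurs in 66% of trials with equal thirds, 67% with 40/40/20, 67% with 60/25/15, 70% with 70/20/10 and 72% with 90/5/5. All three groups are significant in only 0.5–4%. Among trials whose overall complete-case test is significant, 82–94% show the mixed pattern.

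**5. Sensitivity to the effect** (uniform across races, several splits).

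| Placebo vs LACTIN-V | Mixed pattern |
|---|---|
| 45% vs 22.5% | 75–83% |
| 30% vs 15% (design) | 66–72% |
| 45% vs 30% | 54–58% |
| 30% vs 20% | 42–44% |
| 30% vs 30% | about 15% |

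**6. Would removing the p-values be enough?** No. Whether the asymptotic 95% interval for the odds ratio excludes 1 nearly always agrees with the chi-square result. Under the design effect the mixed pattern of excluding and including 1 still occurs in 62–64% of trials at the 50/30/20, 60/25/15 and 40/40/20 splits.

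**7. Which heterogeneity test?** The smallest expected cell in the smallest group is 14 × (27 × 0.15 + 14 × 0.30)/41 = 2.8 at 27/14, and 10 × (21 × 0.15 + 10 × 0.30)/31 = 2.0 at 21/10. In cells this sparse, the ordinary 2-df likelihood-ratio interaction test rejects a uniform effect in 6.2–7.0% of simulated trials. A Woolf homogeneity test with 0.5 correction rejects in about 3% or fewer. The likelihood-ratio test has about 20% power when the effect exists in one group only.

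**8. Count of p-values.** Tables 69 and 70 have 6 × 3 = 18 each, and Tables 71 and 72 have 4 × 3 = 12 each, giving 60.

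**The case against.** The strongest reply is that these are exploratory summaries in a Phase II-b screening trial that openly forgoes multiplicity control. SAP 6.4 speaks of formal tests. Where the SAP wants a formal test it states a null and an alternative, as in 8.1 and 8.2, and it does not do so for race. Per-race proportions with intervals are legitimate description, and nothing in the primary result or the safety analysis depends on these tables.

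Much of this stands. A reader might infer that the race tables contradict SAP 6.4. The documents do not go that far: the tables are labelled exploratory, so this is a tension and an omission from the list of subgroups. A reader might also infer that the sponsor intends to claim race differences from these p-values, but the SAP nowhere proposes that. Nor do the documents show that the Fisher alternative in protocol 11.6.4.1 has been withdrawn. SAP 6.1 names only chi-square for efficacy outcomes, and SAP 13 records no such change.

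The objection leaves the main point untouched. The exploratory label does not alter what the shell prints, and the plan has no result that addresses heterogeneity.

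**Conclusion.** The point holds, as a modest one. As planned, the per-race p-values cannot show whether the effect of LACTIN-V differs by race. If the effect is the design effect in every race, about two thirds of trials would give a mixed pattern, and this changes little across the assumed splits.

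It would be too strong to say that any uniform effect usually produces this pattern. For 30% against 20% it appears in about 42% of trials, and with no effect in about 15%. The calculation concerns BV recurrence by Week 12 with about 205 evaluable women. For Table 70 and the colonization tables (71–72) only the structural criticism applies, because no rates were modelled there. The primary analysis is unaffected.

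**What to change.** - In Tables 69–72, remove the within-race p-values. Keep the per-race proportions and the odds ratios with intervals.
- Add one exploratory treatment-by-race heterogeneity test per population, by a method suited to sparse cells, for example an exact homogeneity test or a Firth-penalised logistic interaction test. The ordinary likelihood-ratio test is not recommended here, given its 6–7% size.
- State beside the tables that this test has low power, so a non-significant result does not show that effects are equal, and that one race's interval excluding 1 while another's does not is not evidence of a race difference. The note is needed because removing the p-values alone leaves most of the mixed pattern visible.
- List race in SAP 6.4 among the exploratory subgroup summaries.

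The cost is one added low-powered model and a shell edit. No new data are needed and the primary analysis does not change.

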2.2 Rationale

This Phase II-b trial is designed to provide a screening evaluation for the hypothesis that, following a 5-day course of MetroGel to treat BV, LACTIN-V administered at 2×10^9 cfu/dose using a vaginal applicator reduces the 12-week incidence of BV recurrence by

≥50% when compared to placebo. Based on the achieved colonization rate of *L. crispatus* CTV-05 at 2×10^9 cfu/dose of LACTIN-V, coupled with prior data from the Phase II-a clinical trial suggesting that vaginal colonization with *L. crispatus* CTV-05 was associated with a reduced risk of BV recurrence, the next logical step is to perform a larger Phase II-b trial.

We plan to enroll 228 women in a 2:1 ratio of LACTIN-V to placebo to estimate the effectiveness of 2×10^9 cfu/dose of LACTIN-V to prevent the recurrence of BV following standard antibiotic treatment with MetroGel and establish longer term safety and acceptability data up to 24 weeks.

The study will be conducted at domestic sites with a known track record of recruiting participants in other BV studies to enable enrollment of all 228 women over 48 weeks. This will allow the study to complete study follow up 18 months after the first woman enrolls in the trial. This timeline assumes that all sites initiate enrollment at about the same time.

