6.1.2 Formulation, Packaging, and Labeling

LACTIN-V and placebo

Each applicator will contain a LACTIN-V powder formulation containing *L. crispatus* CTV-05 at a potency of 2×10^9 cfu/dose. [REDACTED]

. A

matching placebo formulation without *L. crispatus* CTV-05 is supplied in an identical applicator containing placebo powder.

LACTIN-V or placebo pre-filled applicators will be individually packaged in heat-sealed foil pouches, each containing one desiccant packet. Each participant will receive one box containing 25 applicators. Each foil pouch and box will be labeled with the study number and unique participant number.

The foil pouches and boxes will be labeled by the Osel Study Product Supplier. Each label will contain the study number and the FDA-required cautionary statement "*Caution- New drug -Limited by Federal Law to Investigational Use.*" The label of each box of study product applicators will also include the unique participant number and the statements: "*Store at home in a cool, dry place out of reach of children (at room temperature).*"

MetroGel vaginal gel

MetroGel vaginal gel is a gelled purified water solution, containing metronidazole at a concentration of 7.5 mg/g (0.75%). The gel is formulated at pH 4.0. The gel also contains carbomer 934P, edetate disodium, methylparaben, propylparaben, propylene glycol and sodium hydroxide.

MetroGel vaginal gel is supplied in a 70 gram tube. Each participant will receive one box of MetroGel vaginal gel sufficient for the 5-day course of treatment.

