11.6.4.2 Analysis of Secondary Efficacy Outcome Measures

All secondary efficacy outcomes measures will be assessed in the mITT, CC, and PP populations separately.

The secondary efficacy outcome measures are as follows:

1. The proportion of participants experiencing successful colonization with *L. crispatus* CTV-05 following dose of study product through Visit 4 (Week 12, Day 84) in the LACTIN-V arm, overall and stratified by occurrence of menses and intercourse.
2. The proportion of participants experiencing successful colonization with *L. crispatus* CTV-05 following dose of study product at Visit 7 (Week 24, Day 168) in the LACTIN-V arm, overall and stratified by occurrence of menses and intercourse
3. A) The proportion of participants compliant with the dose regimen in each study arm as assessed by participant reporting and applicator staining
B) Summaries from a self-administered questionnaire about acceptability of the study product in each study arm
4. The proportion of participants with a positive BV diagnosis in each study arm by Visit 7 (Week 24, Day 168)

Secondary outcome measures 1 and 2 will be reported within the LACTIN-V arm and across time. The point estimates for the overall proportions and stratified proportions, along with the corresponding standard errors, will be reported. A secondary time-to-event analysis of secondary outcome measure 1 will also be performed, which will be described in the Statistical Analysis Plan.

Secondary Outcome 3A will be reported by study arm. The point estimates for the arm-specific proportions and difference in proportions along with the corresponding standard errors will be reported. Pearson's chi-square test or, if more appropriate, Fisher's exact test, at the 5% two-sided level of significance level without adjustment for multiplicity will be used for the comparisons of proportions between study arms.

For Secondary Outcome 3B, responses to the self-administered questionnaire will be summarized by study arm. Categorical responses will be summarized using contingency tables and/or odds ratios, while continuous responses will be summarized using measures of central tendency such as the mean or median, and measures of dispersion such as the standard deviation or inter-quartile range.

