3.3.3. Successful Colonization of *L. crispatus*

Colonization of *L. crispatus* will be determined from the concentrations of *L. crispatus* species and *L. crispatus* CTV-05 obtained from qPCR. Successful colonization is defined as follows:

- If CTV-05 concentration is above the lower limit of detection (LLOD) and the *L. crispatus* is above the LLOD, then successful colonization has occurred.
- If either CTV-05 or *L. crispatus* concentration is below LLOD or indeterminate, then successful colonization has not occurred.

The LLOD for CTV-05 is 660 copies/mL and the LLOD for *L. crispatus* is 953 copies/mL.

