Table 21 will present the proportion of subjects who experience successful *L. crispatus* colonization at any time post-baseline through Visit 4 (Week 12) (and 95% Wilson confidence interval) in each treatment group along with the odds ratio of *L. crispatus* colonization (and 95% asymptotic confidence interval). A formal hypothesis test will be performed with null hypothesis that the proportion subjects who experience successful *L. crispatus* colonization through Visit 4 (Week 12) in the LACTIN-V group is equal to that in the placebo group and alternative hypothesis that they are not equal. The p-value from the Chi-Square test will be presented. The analyses will be performed in the ITT, mITT, CC, and PP populations, where the ITT and mITT summaries will use the imputation methods described in Section 6.5. Table 22 presents the same summaries for successful *L. crispatus* colonization at Visit 7 (Week 24). Table 23, Table 24, Table 25, and Table 26 present *L. crispatus* colonization by study visit (and 95% Wilson confidence interval) in each treatment group along with the odds ratio of *L. crispatus* colonization (and 95% asymptotic confidence interval). A formal hypothesis test will be performed with null hypothesis that the proportion of subjects who experience successful *L. crispatus* colonization through each visit in the LACTIN-V group is equal to that in the placebo group and alternative hypothesis that they are not equal. The p-value from the Chi-Square test will be presented. Table 27, Table 28, Table 29, and Table 30 presents summary statistics of the concentration of *L. crispatus* CTV-05 by study visit.

Table 31, Table 32, Table 33, and Table 34 will present *L. crispatus* colonization by study day, treatment group, and number of condom-less sexual intercourse acts for each analysis population. The proportion of subjects with colonization along with the 95% Wilson confidence intervals will also be presented. Number of condom-less sexual intercourse acts will be broken up by quartiles from data obtained from the sexual history interview. If the distribution of sexual intercourse acts is such that the use of quartiles does not lead to distinct intervals of values, other cutpoints will be examined (e.g. tertiles, above/below median). Figure 10, Figure 11, Figure 12, and Figure 13 will present *L. crispatus* CTV-05 concentration by study visit, treatment group, number of condom-less sexual intercourse acts, and analysis population.

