Additional summaries of the *L. crispatus* colonization and CTV-05 concentration will be generated as exploratory analyses. Figures of CTV-05 concentration by *L. crispatus* concentration will be generated for each treatment group and study day (Figure 29, Figure 30, Figure 31, and Figure 32). CTV-05 concentration and *L. crispatus* colonization will be further broken down by Amsel criteria and Nugent score. Summaries *L. crispatus* colonization (Yes/No) will be presented by Amsel criteria status (Positive/Negative) (Table 77, Table 78, Table 79, and Table 80) and Nugent score category (Normal/Indeterminate/BV) (Table 81, Table 82, Table 83, and Table 84), following the analyses for Tables 23 - 26. See Section 3.3.1 for Amsel criteria and Nugent score category definitions. Similar summaries will be generated for *L. crispatus* CTV-05 concentration (Table 85, Table 86, Table 87, Table 88, Table 89, Table 90, and Table 91). Boxplots of *L. crispatus* CTV-05 concentration by Amsel Criteria/Nugent Score will be generated for each treatment group and study day (Figure 33, Figure 34, Figure 35, Figure 36, Figure 37, Figure 38, Figure 39, and Figure 40). Listing 6 will provide a listing individual efficacy data.

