		Other	x	x	0.xx	0.xx, 0.xx	--	--	

Continue for mITT, CC, and PP populations

Note: The denominator for rate estimates is based on the number of subjects in the respective treatment group, race group, and analysis population.

1: 95% CI= 95% Wilson confidence interval

2: Difference in 95% CI=asymptotic 95% CI from a Chi-Square test

3: p-value calculated from the Chi Square Test.

Tables with similar format:

Table 72: *L. crispatus* Colonization at Visit 7 (Week 24) by Analysis Population, Treatment Group, and Race

Table 73: *L. crispatus* CTV-05 Concentration by Study Day, Treatment Group, and Race – ITT Population

Study Day (Week)	Treatment Group	Race	Number of Subjects ¹	Mean (SD)	Median	Range
Day 1	LACTIN-V	Black/African American	x	x.xx (x.xx)	x.xx	x.xx, x.xx
		White	x	x.xx (x.xx)	x.xx	x.xx, x.xx
		Other	x	x.xx (x.xx)	x.xx	x.xx, x.xx
	Placebo	Black/African American	x	x.xx (x.xx)	x.xx	x.xx, x.xx
		White	x	x.xx (x.xx)	x.xx	x.xx, x.xx
		Other	x	x.xx (x.xx)	x.xx	x.xx, x.xx
	All Subjects	Black/African American	x	x.xx (x.xx)	x.xx	x.xx, x.xx
		White	x	x.xx (x.xx)	x.xx	x.xx, x.xx
		Other	x	x.xx (x.xx)	x.xx	x.xx, x.xx
Continue for Day 28 (Week 4), Day 56 (Week 8), Day 84 (Week 12), and Day 168 (Week 24)						
1: The number of subjects in the respective treatment group, race group, and analysis population with concentration data available at the specified visit.						

Tables with similar format:

Table 74: *L. crispatus* CTV-05 Concentration by Study Day, Treatment Group, and Race – mITT Population

Table 75: *L. crispatus* CTV-05 Concentration by Study Day, Treatment Group, and Race – CC Population

Table 76: *L. crispatus* CTV-05 Concentration by Study Day, Treatment Group, and Race – PP Population

Table 77: *L. crispatus* Colonization by Study Day, Treatment Group, and Amsel Criteria – ITT Population

Study Day (Week)	Treatment Group	Amsel Criteria	Number of Subjects with Colonization n	Number of Subjects N	Proportion of Subjects with Colonization	Colonization 95% CI	Odds of Colonization in LACTIN-V Group Compared to Placebo Group	Odds of Colonization in LACTIN-V Group Compared to Placebo Group 95% CI	p-value ¹
Day 1	LACTIN-V	Positive	x	x	0.xx	0.xx, 0.xx	x.xx	x.xx, x.xx	0.xxx
		Negative	x	x	0.xx	0.xx, 0.xx	x.xx	x.xx, x.xx	0.xxx
	Placebo	Positive	x	x	0.xx	0.xx, 0.xx	--	--	
		Negative	x	x	0.xx	0.xx, 0.xx	--	--	
	All Subjects	Positive	x	x	0.xx	0.xx, 0.xx	--	--	
		Negative	x	x	0.xx	0.xx, 0.xx	--	--	

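### SAP Tables 77–84 compare LACTIN-V with placebo on colonization by a strain that the placebo lacks; the informative within-LACTIN-V contrast is described but not estimated

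*SAP*

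**What the plan says.** - **Definition (SAP 3.3.3).** A woman is colonized "If CTV-05 concentration is above the lower limit of detection (LLOD") and *L. crispatus* is above its own limit. If either "concentration is below LLOD or indeterminate, then successful colonization has not occurred". Native *L. crispatus* alone cannot count.
- **Placebo (Protocol 6.1.2).** A matching formulation without *L. crispatus* "CTV-05 is supplied in an identical applicator containing placebo powder".
- **Exploratory tables (SAP 8.3).** *L. crispatus* "colonization (Yes/No) will be presented by Amsel criteria status (Positive/Negative") in Tables 77–80 and by Nugent category in Tables 81–84, following Tables 23–26.
- **Inherited method (SAP 8.2).** Tables 21–26 give colonization "in each treatment group along with the odds ratio of" colonization, an asymptotic interval, and a chi-square test that the two arms are equal.
- **Shells (SAP Appendix 1).** Tables 77 and 81 carry the column "Odds of Colonization in LACTIN-V Group Compared to Placebo Group" for each Amsel or Nugent level, from Day 1 onwards. They also give n, N, the colonized proportion and its 95% CI for each level in each arm.
- **Protocol 11.6.4.2.** "Secondary outcome measures 1 and 2 will be reported within the LACTIN-V arm and across time". SAP 3.2.3 likewise defines these outcomes in the LACTIN-V arm. SAP Section 13 lists the added ITT analyses and the changed mITT and CC definitions, but no between-arm colonization test.

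**The concern.** The ratio planned for Tables 77–84 runs between arms, whereas the question these breakdowns raise runs across BV status within the active arm: do women who carry the strain have less BV? Protocol 2.2 gives as part of the trial's rationale that colonization "was associated with a reduced risk of BV recurrence". A between-arm ratio on a marker that only one arm receives cannot address that. It also conditions on Amsel or Nugent status, which is observed after randomization, so it is not a clean randomized comparison.

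The SAP already uses the suitable layout elsewhere. Table 43 compares compliant with non-compliant women within each arm, and Table 50 compares women with and without menses. Tables 77–84 do not follow that form. At stake are ratio, interval and p-value columns that may be blank or uninterpretable, and a colonization–BV relation that readers would have to compute from the printed counts.

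**Working it through.** **Denominators.** The plan's sample size reproduces, and the evaluable numbers follow from it. With 30% on placebo, 15% on LACTIN-V, 2:1 allocation, two-sided 5% and 70% power, the pooled proportion is (0.30 + 2×0.15)/3 = 0.20. Placebo n = [1.96√(0.20×0.80×1.5) + 0.524√(0.30×0.70 + 0.15×0.85/2)]² / 0.15² = 67.7, so 68. Then 68/0.9 = 75.6, so 76, and 76 + 152 = 228. Evaluable: 228×0.9 = 205, or 68 placebo and 137 LACTIN-V.

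**Illustrative inputs (Protocol 2.1 and 11.4).** Colonization is 61% (Phase II-a, ITT). BV recurrence is 12.5% if colonized and 36% if not (capsule trial), and 30% on placebo. Cumulative recurrence stands in for Amsel status.

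- Colonized: 137×0.61 = 84; not colonized: 53.
- BV: 84×0.125 = 10.5, taken as 10; 53×0.36 = 19.
- Placebo: 68×0.30 = 20 with BV, 48 without; none colonized (assumption).

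**The planned contrast**

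| Level | LACTIN-V colonized | Placebo colonized | Odds ratio | With 0.5 added to each cell (95% CI) |
|---|---|---|---|---|
| BV-positive | 10/29 | 0/20 | undefined | 22 (1.2–403) |
| BV-negative | 74/108 | 0/48 | undefined | 210 (12.5–3497) |

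The first corrected value, for example, is (10.5×20.5)/(19.5×0.5) = 22. The SAP gives no zero-cell rule, so the correction is used here only to show scale.

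**Does the ratio respond to the relation of interest?** Suppose colonization were unrelated to BV, with the same overall rate of 29/137 = 21%. The LACTIN-V counts become 18/29 and 66/108, and the corrected ratios are 66 (3.6–1199) and 152 (9.1–2528). They are large either way, with heavily overlapping intervals.

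**If placebo detections are not zero.** With detection rate f, the chance of a zero cell in n women is (1−f)ⁿ. For f = 1%, 2% and 5% (assumed) this is 0.82, 0.67 and 0.36 for n = 20, and 0.62, 0.38 and 0.09 for n = 48.

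**Day 1.** Protocol 7.2 lists the enrollment swabs before the first dose. No colonization is expected in either arm, so the ratio is 0/0.

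**The contrast not printed.** Within LACTIN-V, BV occurs in 10/84 colonized and 19/53 non-colonized women: OR = (10×34)/(74×19) = 0.24, asymptotic 95% CI 0.10–0.58, Fisher p = 0.0012. Rounding 10.5 up to 11 gives 0.27. Assuming 42% or 78% colonization gives 0.25 (0.10–0.62) or 0.24 (0.09–0.61). The contrast is estimable at these sizes.

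**The case against.** A reader might infer that the trial never estimates the colonization–BV relation, or cannot say whether colonization goes with protection. The documents do not support that. The shells print the LACTIN-V colonized count, denominator, proportion and interval at each level. In the illustration those rows are 34% (Wilson 20–53%) of BV-positive and 69% (59–77%) of BV-negative women, and the 0.24 follows from the same four cells because an odds ratio is unchanged by transposing the table. Tables 85–91 and Figures 33–40 also describe CTV-05 concentration by Amsel and Nugent, and Listing 6 shows BV diagnosis beside colonization status. What is missing is a printed contrast, and a table using the combined BV diagnosis of SAP 3.3.1.

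Three further points have weight:

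- No placebo colonization is an inference. The strain is described as naturally occurring, and exclusion criterion 9 exempts LACTIN-V from the bar on prior investigational drugs, so a few placebo positives are possible. Placebo results also serve as a check on assay specificity or contamination. That supports keeping the placebo counts, but it does not make the ratio informative.
- No stated objective commits the trial to estimating this association. The secondary colonization objectives concern menses, intercourse and 24-week persistence. The missing contrast breaks no commitment.
- The illustration mixes 4-week colonization from one trial, symptomatic recurrence from another and an assumed cumulative placebo rate. It implies 21% recurrence on LACTIN-V against the planned 15%, whereas Tables 77–84 are by visit. It shows estimability only and predicts nothing.

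**Conclusion.** The point holds as a minor one. The between-arm odds ratio in Tables 77–84 is non-estimable when a level has no colonized placebo woman, and otherwise mainly reflects product receipt. The first part rests on placebo detection being zero or rare. The second does not need exact zero: with a single placebo positive in each level of the illustration, the ratios are still about 10 and 102. The relation with BV is described within the LACTIN-V arm, but no odds ratio or difference with an interval is planned for it, and none of Tables 77–84 uses the combined diagnosis.

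Tables 21–26 carry the same between-arm contrast, as do the race breakdowns in Tables 71–72. In Tables 21–22 it adds a formal test to outcomes that the protocol reports in one arm, and Section 13 does not declare it. The LACTIN-V proportions that the protocol asks for are still reported, so nothing specified is lost. The primary analysis and the 228 are untouched.

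**What to change.** **Tables 77–84**
- Replace the between-arm odds ratio and p-value with a within-LACTIN-V odds ratio across Amsel level (positive against negative) and Nugent level (4–10 against 0–3, the cut-off in SAP 3.3.1), with an exact CI, in the form of Tables 43 and 50.
- Add a set of rows for the combined BV diagnosis.
- Show placebo as counts only, and omit the ratio at Day 1.
- Label the contrast descriptive, because colonization is a post-randomization variable.

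**Tables 21–26**
- Report the LACTIN-V proportion with its Wilson CI, with placebo counts as a detection check. Alternatively, keep the between-arm test, declare it in SAP Section 13 and use an exact method for zero cells. Tables 71–72 should follow the same choice.

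The cost is SAP wording and column headings in existing shells, with no new data. The small downside is a non-randomized contrast that could be over-read if the label is dropped.
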